Cover Page

**A Randomized Controlled Trial to Evaluate Botulinum Toxin A alone versus Botulinum
Toxin A with hydrodistention for the Treatment of Refractory Overactive Bladder
(HydrA Study)**

NCT02995967

Research Protocol

A Randomized Controlled Trial to Evaluate Botulinum Toxin A alone versus Botulinum Toxin A with hydrodistention for the Treatment of Refractory Overactive Bladder (HydrA Study)

[name], MD¹

[name], MD¹

[name], MD²

[name], MD²

[name], MD¹

[name], MD¹

[name], MD¹

1. Division of Urogynecology and Pelvic Reconstructive Surgery, Department of Obstetrics and Gynecology, University of Alabama Birmingham, Birmingham, AL
2. Department of Urology, University of Alabama Birmingham, Birmingham, AL

Corresponding Author:

[name]

[name]

[name]

[contact]

[contact]

Email: [contact]

FINANCIAL DISCLAIMER/CONFLICT OF INTEREST: NONE

[name]: Protocol/project development, data collection, manuscript writing/editing

Abstract

The specific aim of this randomized, single-blinded controlled trial is to determine if hydrodistention at the time of intradetrusor injection of botulinum toxin A has additional benefit in patients with refractory overactive bladder (OAB) and urgency symptoms compared to intradetrusor injection of botulinum toxin A alone.

Consented patients will be randomized to hydrodistention at a pressure of 80 cm H₂O for 5 minutes, prior to the intradetrusor injection of 100 units of botulinum toxin A (hydrodistention group) or intradetrusor injection of 100 units of botulinum toxin A alone (botulinum toxin A alone group). The primary aim will be subjective improvement measured as change from baseline at 12 weeks using the OAB-q bother subscale. Secondary aims will include number of urgency urinary incontinence (UII) episodes, total number of voids, percentage of patients requiring clean intermittent self-catheterization, elevated post-void residual, health related quality of life, patient global impression of improvement, patient satisfaction, rate of urinary tract infection post-operatively, and 24 week subjective improvement using the OAB-q.

Demographics and baseline data will be analyzed by Student's t-test and chi-squared test or Fisher's Exact test as appropriate.

Specific aims

Primary aim: To determine if hydrodistention at the time of intradetrusor injection of botulinum toxin A has additional symptomatic benefit in patients with overactive bladder (OAB) and urgency symptoms compared to botulinum toxin A injection alone in a single blind, randomized controlled trial using subjective improvement as measured by the OAB-q bother subscale at 12 weeks.

Secondary aims: Secondary aims will include number of urgency urinary incontinence (UII) episodes, total number of voids, proportion of subjects requiring clean intermittent self-catheterization, elevated post-void residual, health related quality of life, patient global impression of improvement, patient satisfaction, rate of urinary tract infection post-operatively, and 24 week subjective improvement using the OAB-q.

Null hypothesis: In subjects with refractory overactive bladder, hydrodistention at the time of intradetrusor injection of botulinum toxin A will result in no difference in OAB-q score compared to botulinum toxin A injection without hydrodistention.

Background

Overactive bladder (OAB) is a common condition that affects approximately 17% of women in the United States [1]. Overactive bladder is defined by the International Continence Society as “urinary urgency, usually accompanied by frequency and nocturia, with or without urgency urinary incontinence, in the absence of urinary tract infection or other obvious pathology” [2]. Approximately one third of these women will have urgency urinary incontinence (UII) with the prevalence increasing with age [1]. The economic burden of this disease is significant with the estimated annual cost of OAB in the United States being \$25 billion [3].

Anticholinergic medications have long been the mainstay of treatment for OAB but have significant side effects including dry mouth and constipation [4] which has led to poor patient compliance and high discontinuation rates in clinical practice [5]. Botulinum toxin A injected into the detrusor muscle during cystoscopy was Food and Drug Administration approved for the treatment of refractory OAB symptoms in 2013. This approval was based on two large randomized controlled trials that included 1,105 patients randomly assigned to placebo or 100

units of intradetrusor botulinum toxin A. A primary endpoint of 12 weeks showed a significant decrease in daily episodes of UUI episodes in the botulinum toxin A group compared to placebo [6,7]. Another double-blind, double-placebo-controlled, randomized trial compared anticholinergic use versus botulinum toxin A which showed a decrease in the number of episodes of UUI in the active group without any significant difference between treatments [8]. In this trial, both groups showed no significant differences in improvement in quality of life, but only 13% of patients in the anticholinergic group and 27% in the botulinum toxin A group reported complete resolution of UUI episodes [8]. Thus, we believe there is much room for improvement in the treatment of OAB symptoms.

Hydrodistention has been a treatment modality for interstitial cystitis (IC) since the early 1900s [9, 10]. It is thought that any efficacy for the treatment of IC is probably related to damage to mucosal afferent nerve endings in the bladder [11]. There are very limited studies on the use of hydrodistention for urgency and OAB symptoms. Dunn et al in a small study found that 14 of 20 patients with urgency and UUI reported resolution of their symptoms after prolonged bladder distention [12]. They also found that the bladder capacity in all patients increased after hydrodistention. In a retrospective review of patients undergoing hydrodistention, Cole et al found that in patients who had undergone the procedure for frequency and urgency symptoms with no pain component, 50% at 1 month, 19% at 3 months, and 7% at 6 months reported improvement in symptoms [13]. Other studies have shown no benefit from hydrodistention in the treatment of urgency and OAB symptoms [14, 15].

There are currently no studies investigating hydrodistention at the time of intradetrusor botulinum toxin A in patients with refractory OAB symptoms. We believe that patients may have additive benefit from a hydrodistention performed with botulinum toxin A injection as the

increased bladder capacity gained by the distention will be sustained for a longer period of time in the setting of botulinum toxin A.

Significance

No studies have been performed examining hydrodistention in the setting of intradetrusor botulinum toxin A for the treatment of refractory OAB symptoms.

Study Design

Inclusion criteria

1. Women with refractory overactive bladder symptoms, failing a credible behavioral therapy intervention and medical therapy or not tolerating medical therapy. Patients who are on medical therapy will stop the medical therapy for at least 2 weeks prior to botulinum toxin A treatment in the study
2. Female \geq 18 years old
3. Desires further treatment for OAB symptoms.
4. Express understanding and ability to perform clean intermittent self-catheterization (CISC) if required.
5. Ability to consent
6. Ability to complete all study related items and interviews

Exclusion Criteria

1. Post void residual urine volume > 150 mL as assessed by catheter or ultrasound
2. History of intradetrusor botulinum toxin A injection
3. History of or current cancer of the genitourinary or gynecology tract

4. Neurogenic bladder
5. Interstitial cystitis
6. Current urinary tract infection (can be treated and re-considered for study)
7. Current active sacral neuromodulation device
8. Non-English speaking
9. History of chronic pelvic pain
10. Hematuria not previously evaluated

Intervention

Hydrodistention at a pressure of 80 cm H₂O for 5 minutes prior to intradetrusor injection of 100 units of botulinum toxin A (hydrodistention group) or intradetrusor injection of 100 units of botulinum toxin A alone (botulinum toxin A alone group).

Primary outcome

The primary outcome will be measured as change from baseline at 12 weeks using the OAB-q bother subscale which consists of eight questions assessing symptom bother with a possible score from 0 to 100 with a higher score indicating greater symptom bother.

Secondary outcomes

1. Number of UUI episodes as reported in a 3-day bladder diary at 12 weeks as measured in change from baseline.
2. Total number of voids reported in the 3-day bladder diary at 12 weeks as measured in change from baseline.

3. Proportion of subjects requiring clean intermittent self-catheterization (CISC) post-operatively as reported at 2 week post-operative visit. CISC will be initiated at post-void residual volumes of > 300 mL *or* > 150 mL in the presence of bothersome retention symptoms.
4. Post-void residual volume (PVR) at the 2 week follow-up visit measured with catheter or bladder scan.
5. Rate of urinary tract infection (UTI) as assessed by positive urine culture in patients having symptoms (dysuria, urgency, frequency, temperature ≥ 38 degrees Celcius, and/or suprapubic pain) at the 2 weeks post-operative visit. Subjects who call throughout the study complaining of symptoms but are unable to give a urine culture in clinic will also be treated and reported as having had a UTI.
6. Health related quality of life (HRQL) will be measured as a change from baseline at 12 weeks using the OAB-q HRQL subscale part which consists of 25 questions that assess HRQL addressing coping, concern, sleep, and social interaction where the scoring scale is from 0 to 100 with a higher score indicating a better quality of life.
7. Patient global impression of improvement at 12 weeks as measured using the Patient Global Impression of Improvement Questionnaire (PGI-I).
8. Patient satisfaction at 12 weeks as measured using Patient Satisfaction Questionnaire (PSQ).
9. Subjective outcome at 24 weeks using the OAB-q

Protocol in detail

Women seen in the urogynecology and urology clinics at University of Alabama at Birmingham who are seeking treatment for refractory OAB symptoms will be screened. Patients

who have failed a credible behavioral therapy intervention and medical therapy or not tolerating medical therapy will be evaluated for this study. Those patients satisfying the inclusion/exclusion criteria will be offered to participate in the study. Informed consent will be reviewed and signed with patients wishing to proceed.

At enrollment, any subjects who are using medical therapy including anticholinergic or β_3 agonist medications will stop these therapies for at least 2 weeks prior to treatment. Baseline clinical data including OAB-q and a 3 day bladder diary will be collected as well as clinical and demographic information. Data from subjects' urodynamic testing will be abstracted from the clinical chart if performed within the prior 12 months of the enrollment date. If no urodynamics testing is available then we will not collect this information for those subjects. Subjects will also be counseled on the possible need for clean intermittent self-catheterization (CISC) and instructions on how and when to perform CISC will be given in clinic. Subjects will be randomized the day of the scheduled procedure. Subjects will be blinded to which group they are assigned.

Subjects randomized to the botulinum toxin A alone group will undergo intradetrusor injection of 100 units of botulinum toxin A diluted in 10 cc of sterile normal saline and injected in volumes of 0.5cc in a grid-like pattern using rigid cystoscopy in the operating room under monitored anesthesia care (MAC) or general anesthesia. Those subjects randomized to the hydrodistention group will undergo hydrodistention of the bladder in the operating room just prior to the botulinum toxin A injection. The hydrodistention will be performed with a water pressure of 80 cm H₂O as measured by the height of the sterile water source above the pubic symphysis in the operative room. The bladder will be filled and noted to be full as evidenced by no further influx of water into the bladder. The bladder will be emptied and this volume will be

recorded as initial bladder volume. The hydrodistention will then be performed with the bladder filled at a pressure of 80 cm H₂O and noted to be full as evidenced by no further influx of water into the bladder. This volume will be held in the bladder for 5 minutes. Upon emptying, the volume will be recorded as the hydrodistention volume. After the hydrodistention, these subjects will then receive intradetrusor injection of 100 units of botulinum toxin A in a grid like pattern using rigid cystoscopy as described above.

Subjects will be seen for a 2 week post-operative visit. It will be recorded if subjects have had to use CISC including how many days. CISC will be initiated at post-void residual volumes of > 300 mL *or* > 150 mL in the presence of bothersome retention symptoms. Subjects with symptoms of UTI including dysuria, urgency, frequency, temperature \geq 38 degrees Celsius and/or suprapubic pain will have urine culture sent and treated accordingly for UTI. If subjects call with symptoms of urinary tract infection but are unable to present for urine culture will also be treated and reported as an UTI.

Subjects will follow up for scheduled post-operative care at a 6 and 12 weeks at which time they will complete the OAB-q, PGI-I, and PSQ for the 12 week primary outcome data. Subjects will complete a 3 day bladder diary during the week prior to the 12 week visit and bring the information with them to the visit. At the 24 week follow up visit, patients will complete the OAB-q. All follow up visits at 2 weeks, 6 weeks, 12 weeks, and 24 weeks will be plus or minus a 1 week window from the date of procedure.

Randomization/Allocation

Patients will be randomized to the hydrodistention group or botulinum toxin A alone group in a 1:1 fashion using variable size permuted blocks of 4, 6, and 8. This will be done by a

member of the research team on the day of the procedure. Subjects will be blinded to which group they are assigned. Allocation concealment will be ensured by using a centralized service to provide sequentially numbered, opaque, sealed envelopes.

Confidentiality

Extensive efforts will be made to ensure and maintain participant confidentiality. All identifying information will be maintained in a secure area at all times. Participants will be assigned a Study ID number at study enrollment taken from the randomization log. This Study ID will be used to label all data collection sheets.

Power analysis

A sample size of 27 patients per group provides 80% power to detect a difference of 15 points or more at a 0.05 level of significance. For this determination, we estimated the mean OAB-q bother score in the control group to be 45 and the standard deviation of the change in severity scores to be 19 points based on a prior studies by Coyne, et al [16, 17]. We hypothesized a 15 point difference to be meaningful based on feasibility, clinical significance, and prior reported minimally important difference (MID) [17]. Allowing for a 10% dropout rate, we will recruit a total of 60 patients, 30 per group.

Data analysis

Demographics and baseline data will be analyzed by Student's paired t-test and chi-squared test or Fisher's Exact test as appropriate.

Project schedule

- February to May 2016: start up and obtain IRB approval

- May 2016 until August 2017: Recruitment and Enrollment
- September 2017 to March 2018: Data analysis, manuscript completion

References for OAB Hydro

2. Haylen BT, de Ridder D, Freeman RM, et al. An International Urogynecological Association (IUGA)/International Continence Society (ICS) joint report on the terminology for female pelvic floor dysfunction. *Int Urogynecol J*. 2010;21:5.

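### The plan names no test for the primary comparison; prespecifying ANCOVA with baseline OAB-q bother as covariate would be a low-cost gain in precision over the implied unadjusted change score

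*Combined protocol and SAP*

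**What the plan says.** Under Primary outcome: "The primary outcome will be measured as change from baseline at 12 weeks using the OAB-q bother subscale". The Abstract says the same: "The primary aim will be subjective improvement measured as change from baseline at 12 weeks using the OAB-q bother subscale".

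The whole Data analysis section is one sentence: "Demographics and baseline data will be analyzed by Student's paired t-test and chi-squared test or Fisher's Exact test as appropriate". The Abstract has a sentence of the same scope, without the word paired. Neither reaches the primary outcome, and no other section names a test, model or covariate for it. The null hypothesis under Specific aims speaks of OAB-q score rather than change, and names no test.

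The nearest thing to an analysis is the Power analysis, which takes "the standard deviation of the change in severity scores to be 19 points" and concludes: "A sample size of 27 patients per group provides 80% power to detect a difference of 15 points or more". It then adds: "Allowing for a 10% dropout rate, we will recruit a total of 60 patients, 30 per group". These inputs imply a two-sample comparison of mean change without covariates, but the plan does not say so.

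The covariate is available. Protocol in detail says: "Baseline clinical data including OAB-q and a 3 day bladder diary will be collected".

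**The concern.** Two things follow from the silence on the primary test.

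First, the choice among a change score, a raw 12-week score and a baseline-adjusted score is left open until the data are in. Each is valid by itself, but choosing among them after seeing results is not.

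Second, the one comparison that can be inferred makes limited use of the baseline. An unadjusted change score fixes the slope on baseline at 1. ANCOVA estimates that slope, and its residual variance is lower whenever baseline is correlated with change. With about 27 evaluable women per arm, and no stratification on baseline severity described under Randomization/Allocation, any gain would matter for the width of the confidence interval on the main result.

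**Working it through.** **Inputs.** From Power analysis: difference 15, SD of change 19, 27 evaluable per arm, significance level 0.05, 10% dropout. The section does not say whether the test is one- or two-sided. Two-sided is assumed, because a one-sided test would need only about 20 per arm by the normal approximation. The documents do not give the correlation c between baseline and change, so c is varied as an assumption.

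**Step 1: the plan's own figure.** Two-sample t-test on change:

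- SE = 19 × √(2/27) = 5.17; noncentrality = 15/5.17 = 2.90; df = 52.
- Noncentral-t power is 81.2% at 27 per arm and 79.7% at 26, so 27 is the smallest size that reaches 80%.
- The 95% CI half-width is 2.007 × 5.17 = 10.4 points.
- Dropout: 27/(1 − 0.10) = 30 per arm, 60 in total.

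The sizing reproduces.

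**Step 2: ANCOVA with the same inputs.** Residual SD = 19 × √(1 − c²); df = 2 × 27 − 3 = 51. Estimating the slope multiplies the variance of the treatment difference by 1 + 1/50 on average over chance baseline imbalance.

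| Absolute value of c (assumed) | Residual SD | SE | Power | Change from 81.2% |
|---|---|---|---|---|
| 0 | 19.0 | 5.22 | 80.4% | −0.8 points |
| 0.2 | 18.6 | 5.12 | 82.0% | +0.8 |
| 0.3 | 18.1 | 4.98 | 84.0% | +2.8 |
| 0.5 | 16.5 | 4.52 | 90.2% | +9.0 |

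At c = 0 the half-width is 2.008 × 5.22 = 10.5 points; at 0.5 it is 2.008 × 4.52 = 9.1.

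Break-even is close to the point where (1 − c²) × 1.02 = 1, which gives c = 0.14. The exact power calculation agrees.

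**Step 3: what c could be.** Let r be the ratio of the 12-week SD to the baseline SD, and ρ the correlation between the two scores. Then c = (ρr − 1)/√(1 + r² − 2ρr). With r = 1 (assumed), ρ of 0.9, 0.5 and 0.3 gives power of 82.4%, 90.2% and 93.8%. With r = 1.25 and ρ = 0.8, ρr = 1, so c = 0 and ANCOVA has the 0.8-point loss. Both outcomes are possible, and the documents do not settle which applies.

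**Step 4: how far the 0.8-point figure holds.** It is an average at the planned inputs. With c = 0, the average loss is about 1.0 point with 24 evaluable per arm, about 0.9 with an SD of 22 at 27 per arm, and about 0.6 with 30 per arm. If a particular randomization leaves the arms 0.5 SD apart at baseline, the loss conditional on that is 2.5 points.

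**Step 5: why the choice should be fixed in advance.** Null simulation with 27 per arm, equal SDs and ρ of 0.3, 0.5 and 0.7 (assumed), 40,000 trials each: every method alone has type I error of about 5%. Taking the smaller p-value of change score and ANCOVA gives 6.7% to 7.6%. Choosing among those two and the raw 12-week score gives 9.0% to 9.9%.

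**The case against.** The strongest reply is that the missing test and the preference for ANCOVA are separate matters. Naming a two-sample t-test on change, as the sizing implies, would fully cure the missing prespecification. The danger of choosing after the fact argues for fixing any test in advance, not for ANCOVA in particular. That stands. The case for ANCOVA rests only on precision, and the documents cannot say how much would be gained. It also stands that ANCOVA is not the only reasonable model: OAB-q is also completed at 6 weeks, and a repeated-measures model could use that visit.

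Four stronger readings are tempting, and the documents support none of them.

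- A reader might infer that the unadjusted change score is biased or leaves the trial underpowered. Under randomization it is valid, and it has 81.2% power at the stated inputs.
- A reader might take 0.8 points as a ceiling on the possible loss. It is an average at 27 per arm, SD 19 and difference 15, as Step 4 shows.
- A reader might take the t-test sentence in Data analysis as the primary analysis. Its wording confines it to demographics and baseline data.
- A reader might extend the same recommendation firmly to the diary outcomes, for example "Number of UUI episodes as reported in a 3-day bladder diary at 12 weeks as measured in change from baseline". Urgency incontinence is not an entry requirement, and the Background puts it at about one third of women with OAB, so counts may contain many zeros. The documents do not give their distribution.

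**Conclusion.** The point holds as a recommendation. No primary test is prespecified, and baseline-adjusted ANCOVA is a better default than the unadjusted comparison the sizing implies. It uses data already collected and gives the same treatment estimate whether the response is the 12-week score or the change. That also removes the ambiguity between the null hypothesis and the outcome definition.

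The trade is a small average loss if baseline tells nothing about change, against a gain above a correlation of about 0.14. At the planned inputs the worst average case, 80.4%, still meets the stated 80%. That last statement depends on dropout staying within the planned 10% and on the SD of 19. Confidence is high that the test is missing and that the cost is small. It is not high about the size of the benefit.

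**What to change.** Add to Data analysis that 12-week OAB-q bother (equivalently, its change from baseline) will be compared between randomized groups by ANCOVA with baseline OAB-q bother as covariate, reporting the adjusted mean difference, 95% CI and two-sided p-value.

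Apply the same model to the 12-week OAB-q HRQL subscale with its own baseline. For 24 weeks, Secondary outcomes names only the OAB-q. State the subscale and, if it is bother, use the same model with baseline bother as covariate. Baseline-adjusted ANCOVA for the two diary outcomes is optional.

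Keep 27 evaluable and 30 recruited per arm, so that the sizing does not lean on an unknown correlation.

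The cost is a few sentences and one degree of freedom, with the average power loss given above if baseline proves uninformative. No new data, visits or patients are needed.

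### Secondary outcome 1 uses the baseline UUI count only by subtraction; adjusting for it, with an interval that allows unequal slopes, would give a more precise estimate at almost no cost

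*Combined protocol and SAP*

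**What the plan says.** Secondary outcomes, item 1, is "Number of UUI episodes as reported in a 3-day bladder diary at 12 weeks as measured in change from baseline". Both diaries are planned. In Protocol in detail, "Baseline clinical data including OAB-q and a 3 day bladder diary will be collected as well as clinical and demographic information" at enrollment, and later "Subjects will complete a 3 day bladder diary during the week prior to the 12 week visit". Randomization is on the day of the procedure, so the baseline count precedes allocation and is a legitimate covariate.

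The entry population is "Women with refractory overactive bladder symptoms, failing a credible behavioral therapy intervention and medical therapy or not tolerating medical therapy". None of the six inclusion or ten exclusion items asks for a UUI episode, and the definition of OAB in the Background is "usually accompanied by frequency and nocturia, with or without urgency urinary incontinence".

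The Data analysis section is a single sentence: "Demographics and baseline data will be analyzed by Student's paired t-test and chi-squared test or Fisher's Exact test as appropriate". It gives no test, model or covariate for this or any other 12-week outcome.

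**The concern.** There are two separate issues.

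- **Precision.** A change score fixes the weight on baseline at one. If treatment lowers the counts substantially, the baseline count varies more than the 12-week count, and full subtraction adds noise. The raw comparison of change is still valid, but it is less precise than an adjusted analysis of the same data.
- **Dilution.** A woman with no episodes on the baseline diary cannot improve on this measure. The more such women enroll, the smaller the all-subject difference. Without the number of zero-baseline women by arm, a reader cannot tell a lack of effect from a shortage of incontinent women.

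Adjustment addresses the first issue and does not undo the second. At stake is how well one unpowered secondary outcome is estimated and read.

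**Working it through.** **The plan's own figure.** The Power analysis gives 27 per group for a 15-point difference, SD 19 and 80% power at 0.05 (two-sided assumed). Noncentral t gives 79.7% at 26 and 81.2% at 27; 27/0.9 = 30 per group, 60 in total. The figure reproduces. It concerns the primary outcome, and no size or power is stated for UUI.

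**Direction of the gain.** Let r be the baseline/12-week correlation and q = SD(12 weeks)/SD(baseline). In units of SD(baseline)²:

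- Var(change) = 1 + q² − 2rq
- Var(ANCOVA residual) = q²(1 − r²)
- Difference = (1 − rq)², which is never negative.

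At r = 0.5 and q = 0.5 these are 0.75, 0.1875 and 0.5625, so the SD ratio is √(0.1875/0.75) = 0.50. For q = 0.7, 0.9 and 1.0 the ratio is 0.68, 0.82 and 0.87. The gain vanishes as rq nears 1.

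**Size of the gain.** The documents give no UUI mean, SD, correlation or wet fraction p, so every input here is assumed:

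- 27 per arm;
- wet women's baseline rate gamma (shape 1.5, mean 10 per 3 days), with at least one episode counted;
- 12-week count negative binomial with dispersion 1;
- dry women zero at both visits;
- 6,000 runs, p from 1/3 to 1.

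Results for common-slope ANCOVA with ordinary errors against raw change:

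| Episodes remaining, control v hydrodistention | SD ratio | Power, raw/ANCOVA, p = 1/3 | Power, raw/ANCOVA, p = 1 |
|---|---|---|---|
| 50% v 25% | 0.57-0.70 | 0.08/0.11 | 0.21/0.39 |
| 65% v 40% | 0.72-0.85 | 0.07/0.08 | 0.17/0.22 |
| 80% v 60% | 0.86-0.93 | 0.056/0.055 | 0.106/0.108 |

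Null rejection was 0.034-0.049 for this model, so the test is sound under no effect.

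**Interval coverage when there is an effect.** A proportional effect makes the baseline slope differ by arm. Nominal 95% intervals from the common-slope model then covered 0.875-0.924 at 50% v 25%, 0.891-0.942 at 65% v 40% and 0.939-0.950 at 80% v 60%; raw change covered about 0.95. At p = 1/3 and 50% v 25% the common-slope estimate was also shrunk, −0.80 against −0.88. HC3 errors on the common-slope model repaired this only partly (0.889-0.933 at 50% v 25%).

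Arm-specific slopes with HC3 errors covered 0.925-0.963 wherever there was an effect, largely removed the shrinkage, and kept most of the SD reduction at 50% v 25%. Against the raw t-test, power for this form went from 0.073 to 0.085 at p = 1/3 and from 0.215 to 0.305 at p = 1 for 50% v 25%. It was unchanged at 65% v 40% and slightly lower at 80% v 60%. Null rejection was 0.018-0.037, which is conservative.

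**Dilution.** At 50% v 25% the effect in wet women is about (0.25 − 0.50) × 10 = −2.5 episodes. Across all subjects it is about p times that: −0.83, −1.25, −1.75 and −2.25 at p = 1/3, 0.5, 0.7 and 0.9. The simulated common-slope estimates were −0.80, −1.22, −1.76 and −2.29. Chance imbalance matters too: in a second simulation under different assumptions, with 20%, 40% and 67% dry, the arms differed by five or more dry women in about 12%, 20% and 19% of trials.

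**The case against.** **The plan does use the baseline count.** Correct. A reader might infer that it is ignored, but it enters the outcome by subtraction and falls within the baseline data to be analyzed. What stands is narrower: no outcome analysis adjusts for it.

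**The plan never chose an unadjusted t-test.** Also correct. A reader might infer that a weak method was selected, but no method is stated for any outcome. Raw change is the natural reading of item 1 and serves here only as the comparator.

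**ANCOVA is a free gain.** This stronger reading is tempting and fails. With ordinary errors and one slope, the interval under-covers mainly where the power gain is largest, and most when many women are dry.

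**The size is all assumption.** Largely so. With all women wet and 40% v 20% of episodes remaining, common-slope ANCOVA power was 0.95, 0.80, 0.58, 0.38 and 0.21 at dispersion 0, 0.2, 0.5, 1 and 2, against 0.12-0.20 for raw change. The documents do not say which case applies. The Background's report that "27% in the botulinum toxin A group reported complete resolution of UUI episodes" does not settle it: simulated shares of wet women at zero were 24% (50% remaining, dispersion 1) and 29% (80% remaining, dispersion 2). Its one-third share with UUI describes women with OAB generally, not refractory clinic patients, so p = 1/3 is only the outer end of a range.

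**The zero-baseline count is a reporting detail.** On its own, yes. It is proposed as a companion to the estimate, and its absence from a short protocol is not an error.

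**Conclusion.** The point holds as a minor improvement. Secondary outcome 1 uses the baseline count only by subtraction, and the plan states no adjusted comparison although the count is collected before randomization. In large samples linear adjustment cannot lose precision against raw change, whatever the inputs. How much it gains depends on assumed rates, dispersion and wet fraction: substantial if counts fall well below baseline, small at 80% v 60%.

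With an interval that remains near nominal, the power gain ranges from modest at 50% v 25% to slightly negative at 80% v 60%. The benefit is therefore mainly a more precise estimate, not a better chance of significance. A reader might infer that adjustment rescues the outcome when many women are dry. It does not, because dilution remains. Nothing here bears on the primary outcome or the 60-subject sample size.

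**What to change.** Add to Data analysis, before any unblinded comparison:

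1. In all randomized subjects with diary data, regress the 12-week 3-day UUI count on arm, the mean-centred baseline count and their interaction. Report the arm coefficient as the average difference, with HC3 errors that also allow for estimating the baseline mean: add (interaction coefficient)² × Var(baseline)/N to the HC3 variance. Using the change as the response gives the same arm estimate, because subtracting baseline only shifts the common slope by one; item 1 need not be redefined.
2. Report the number with zero baseline episodes by arm and, as a descriptive companion, the same estimate in women with at least one. That estimate rests on about 18, 27, 38 or 49 of 54 women at p = 1/3, 0.5, 0.7 or 0.9.
3. Keep all subjects in the main analysis. A zero on one 3-day diary may misclassify a woman who leaks, and the protocol does not say whether the baseline diary falls before or after medication is stopped.

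The cost is wording only: no new data, visits or subjects. The statistical price is two degrees of freedom against the two-sample t-test (54 − 4 = 50 instead of 54 − 2 = 52), a conservative test under no effect, and a slight loss of power if counts fall little.
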